## 14.6. Study Monitoring

Throughout the course of the study, the study monitor will make frequent contacts with the investigator. This will include telephone calls and on-site visits. During the on-site visits, the eCRFs will be reviewed for completeness and adherence to the protocol. As part of the data audit, source documents will be made available for review by the study monitor. The study monitor will also perform drug accountability checks and may periodically request review of the investigator study file to ensure completeness of documentation in all respects of clinical study conduct. As part of study-related monitoring, data audits, IRB/IEC review, and regulatory inspections, the investigator(s)/institution(s) will provide direct access to source data/documents.

Upon completion of the study, the study monitor will arrange for a final review of the study files after which the files should be secured for the appropriate time period. The investigator or appointed delegate will receive the study monitor during these on-site visits, will cooperate in providing the documents for inspection, and will respond to inquiries. In addition, the investigator will permit inspection of the study files by authorized representatives of the regulatory agencies.

## 14.7. Quality Assurance

The study will be conducted in accordance with NBI's standard operating procedures designed to ensure that all procedures are in compliance with GCP and FDA Guidelines, and according to the laws and regulations of the country in which the study is conducted. Quality assurance audits may be performed at the discretion of NBI.

#### 14.8. Record Retention

Study records should be retained in compliance with the federal, national, and/or local regulations of the clinical site.

NBI may request these records to be retained for a longer period if required by applicable regulatory requirements or Sponsor contractual obligations. If the investigator is unable to retain the study documents for the required amount of time, NBI must be informed of the individual who will be assuming this responsibility.

## 14.9. Confidentiality

NBI or its designee, and the study center affirm and uphold the principle of the subject's right to protection against invasion of privacy. Throughout this study, all data will be identified only by an identification number.

All information concerning this study and which was not previously published is considered confidential information. This confidential information shall remain the sole property of NBI; it shall not be disclosed to others without written consent of NBI; and shall not be used except in the performance of this study.

The information compiled during the conduct of this clinical study is also considered confidential and may be disclosed and/or used only by NBI as deemed necessary. To allow the use of the information derived from this clinical study and to ensure compliance to current federal regulations, the investigator is obliged to furnish NBI with the complete test results and all data compiled in this study.

#### 15. STUDY COMMENCEMENT AND DISCONTINUATION

Upon satisfactory receipt of all required regulatory documents, NBI (or designee) will arrange that all study materials be delivered to the study site. Subject enrollment should not begin until after the required regulatory documents are confirmed as received and the Investigator Meeting/Initiation Meeting has occurred. All personnel expected to be involved in the conduct of the study will undergo orientation to include review of the study protocol, instructions for eCRF completion, AE reporting, and overall responsibilities including those for drug accountability and study file maintenance.

If the study is discontinued, all subjects should undergo a complete follow-up examination. Any clinically relevant finding, including laboratory values of potential clinical concern, and adverse experiences will be followed until they resolve or return to a clinically acceptable level.

## APPENDIX A. GLUCOCORTICOID STRESS DOSING GUIDANCE

Extra glucocorticoid (eg, hydrocortisone) must be given during times of **extreme physical stress** such as fever, vomiting and diarrhea, surgery, and significant trauma (eg, broken bones and concussions) (CARES Foundation, 2014; Miller et al., 2020; National Institutes of Health). The fludrocortisone dose does not need to be changed.

Type of Illness	Instruction		
Minor illness or low-grade fever >100.5°F (38°C):	Double the hydrocortisone dose for the entire day, until fever or symptoms subside. Drink extra fluids (sugar- and salt-containing).		
Moderate illness or fever ≥102°F (39°C)	Triple the hydrocortisone dose for the entire day (administered in 3 to 4 divided doses over the day) until fever or symptoms subside.  Drink extra fluids (sugar- and salt-containing).		
Vomiting	Triple the hydrocortisone dose.  If vomiting occurs <30 minutes after taking the dose, wait 15 to 30 minutes and repeat the dose since it was likely not absorbed.  If vomit again, administer injectable hydrocortisone (Solu-Cortef) (see below) and contact treating physician. Do not delay in giving injectable hydrocortisone.		
Diarrhea	If no fever and feeling well, no need for stress dosing.  If not feeling well, double the hydrocortisone dose.  Drink extra fluids (sugar- and salt-containing).		
All illnesses	To prevent dehydration, drink extra sugar and salt-containing fluids (eg, nondiet soda, Gatorade, popsicles, soup).		
For minor surgical procedures not requiring general anesthesia	Triple the morning glucocorticoid dose.		
Not tolerating oral medications or unconscious	Administer injectable (eg, intramuscular) hydrocortisone (Solu-Cortef) at 50 to 100 mg/m² or doses below and contact the treating physician.  <3 years: 25 mg 3-12 years: 50 mg  >12 years: 100 mg  If unable to tolerate fluids or unconscious, contact emergency services for evaluation following injectable hydrocortisone treatment.		

- 1. Signs of acute cortisol deficiency (adrenal crisis) include, but are not limited to: headache, nausea, vomiting, abdominal pain, dehydration, confusion, weakness, lethargy, pallor, fatigue, dizziness, hypotension, hypoglycemia.
- Prevention of adrenal crisis: The injectable form of hydrocortisone (Solu-Cortef) must be kept at home and at school for emergencies. It may be kept in a medication cabinet for several years in the unmixed form. Check the expiration date and get a prescription refill when needed.
- 3. Call the treating physician for any of the following:
  - a. Elevated temperature above  $102\Box F$  (39 $\Box C$ )
  - b. Fever for more than 3 days
  - c. Difficulty waking your child
  - d. Change in behavior such as acting confused
  - e. Vomiting and unable to keep down medication
  - f. Whenever hydrocortisone injection (Solu-Cortef) is given
- 4. Dexamethasone is not suitable for treatment of salt-wasting adrenal crisis because it has no mineralocorticoid effect. Methylprednisolone (10 to 25 mg/m2/dose) may be used to treat adrenal crisis although it has less mineralocorticoid activity than hydrocortisone. Hydrocortisone in high doses has mineralocorticoid effect, and thus no fludrocortisone is needed during intravenous stress dosing.

## APPENDIX B. CRINECERFONT DOSE ADJUSTMENT GUIDANCE (AFTER MONTH 12/WEEK 52)

Guidance on changes to crinecerfont dosing in the OLE is provided in the table below.

During the OLE, subjects may have their glucocorticoid doses adjusted as appropriate and tolerated to achieve the lowest glucocorticoid dose that maintains adequate disease control (in the opinion of the investigator). The glucocorticoid dose reduction will not require dose reduction below 8 mg/m²/day hydrocortisone equivalents.

In the setting of inadequate efficacy (in the opinion of the investigator), if the glucocorticoid dose is at or above the target, an increase in the glucocorticoid dose should generally be considered only after the crinecerfont dose has been maximized for the subject (ie, the evening dose has been doubled). Changes to the glucocorticoid and crinecerfont doses should generally be separated by at least 1 month in order to assess the effect of each change. Changes to the crinecerfont dose (whether based on crossing into the next weight category or based on inadequate efficacy) should generally only be made at scheduled study visits.

## **Guidance for Dose Adjustment During the Open-Label Extension**

Type of Change in Crinecerfont Dosing During OLE	Applicable Study Visits	Examples	Additional Guidance
Formulation switch: oral solution versus capsule, based on subject preference (only subjects receiving 50 mg bid or higher)	Month 12/Week 52	• 50 mg bid solution in core study but prefer capsule → switch to 50 mg bid capsule at Month 12.	• If there is a tolerability issue on the new formulation (eg, difficulty swallowing capsule), the subject can revert back to previous formulation (ideally within approximately 1 month).
			
 
Once formulation preference is established at or within approximately 1 month of Month 12, formulation should remain the same for the rest of the OLE.
 

			• The 25 mg bid dose regiment remains as solution (no option for 25 mg via capsule).
			
 
Change in formulation may occur in conjunction with weight-based adjustment or increase for inadequate efficacy.
 

Weight-based adjustment in dose when subject's body weight increases such that subject crosses into the next weight category 10 to <20 kg: 25 mg bid 20 to <55 kg: 50 mg bid ≥55 kg: 100 mg bid	Month 12/Week 52 and every 6 months thereafter during OLE	• 50 mg bid based on weight 20 to <55 kg in core study, which increases to ≥55 kg in OLE → adjust dose to 100 mg bid based on new weight category (even if efficacy assessed as inadequate at the same time).	
 
An increase in dose based on new weight category should be done first before increasing dose for inadequate efficacy if both conditions apply.
 
If weight decreases into a lower weight category, no dose adjustment is necessary unless there is a tolerability issue.
 

Dose increase for inadequate efficacy by doubling the evening dose	Once per weight category starting at Month 12 and any	on 50 mg bid and subject remains in the same weight category $\rightarrow$ increase to 50 mg qam, 100 mg	• If the crinecerfont dose is increased for inadequate efficacy, a study visit is performed approximately 1 month after dose increase for efficacy, PK, and safety assessments.
• 25 mg bid → 25 mg qam, 50 mg qpm	subsequent visit during the OLE		
 
If there is a tolerability issue with the crinecerfont dose increase, the dose can be decreased back to prior dose.
 


 
50 mg bid → 50 mg qam, 100 mg qpm
 
100 mg bid → 100 mg qam, 200 mg qpm
 
			
 
If there is a need to decrease the crinecerfont dose back to the prior dose based on tolerability, the dose should not be increased again for inadequate efficacy during the rest of the OLE.
 

			
 
If subject weight crosses into the next weight category after increasing for inadequate efficacy, adjust the crinecerfont dose for weight first.
 

bid=twice daily; OLE=open-label extension; PK=pharmacokinetic; qam=in the morning, qpm=in the evening.

#### CONFIDENTIAL

NCT04806451

Version Number	Date	Author(s)	Page Number	Modification(s)
1.0	08 August 2023		N/A	N/A
2.0	18 September 2023		24	The definition of the baseline and Week 4 serum androstenedione values have been updated from the average of all serial sampling values to the average of the pre-morning glucocorticoid dose values.
2.0	18 September 2023		24	The definition of the baseline and Week 4 serum 17-OHP values have been updated from the average of all serial sampling values to the average of the pre-morning glucocorticoid dose values.
2.0	18 September 2023		43	The supplemental analysis using the average of the pre- morning glucocorticoid dose values of serum androstenedione has been updated to use the average of all serial sampling values.
2.0	18 September 2023		45	The supplemental analysis using the average of the pre- morning glucocorticoid dose values of serum 17-OHP has been updated to use the average of all serial sampling values.

## LIST OF ABBREVIATIONS

Abbreviation	Term
17-OHP	17-hydroxyprogesterone
АСТН	Adrenocorticotropic hormone
AE	Adverse event
ANCOVA	Analysis of covariance
ATC	Anatomic Therapeutic Chemical
BID	Twice daily
BLQ	Below the lower limit of quantification
BMI	Body mass index
BPRS-c	Brief psychiatric rating scale for children
BSA	Body surface area
САН	Congenital adrenal hyperplasia
CI	Confidence interval
СМН	Cochran-Mantel-Haenszel
CSR	Clinical study report
C-SSRS	Columbia-Suicide Severity Rating Scale
DB	Double-blind
DMC	Data Monitoring Committee
ECG	Electrocardiogram
eCRF	Electronic case report form
EDC	Electronic data capture
EQ-5D-5L	EuroQoL 5 Dimensions 5 Levels
EQ-5D-Y	EuroQoL 5 Dimensions Youth
FAS	Full analysis set
FCS	Fully conditional specifications
FDA	Food and Drug Administration
FSH	Follicle stimulating hormone
GC	Glucocorticoid
GTT	Glucose tolerance test
HDL	High-density lipoprotein

Abbreviation	Term
HOMA-IR	Homeostatic model assessment of insulin resistance
HRQL	Health-related quality of life
HTN	Hypertension
ІСН	International Council for Harmonization
IPD	Important protocol deviation
IRT	Interactive response technology
IUD	Intrauterine device
LDL	Low-density lipoprotein
LH	Luteinizing hormone
LLN	Lower limit of normal
MedDRA	Medical Dictionary for Regulatory Activities
MI	Multiple imputation
NBI	Neurocrine Biosciences, Inc.
OL	Open-label
OLE	Open-label extension
PDHP	Protocol Deviation Handling Plan
PedsQL	Pediatric Quality of Life Instrument
PKAS	PK analysis set
PRA	Plasma renin activity
РТ	Preferred Term
QD	Daily
QID	Four times per day
SAE	Serious adverse event
SAP	Statistical analysis plan
SAS	Safety analysis set
SD	Standard deviation
SDS	Standard deviation score
SE	Standard error
SEM	Standard error of the mean
SMQ	Standardized MedDRA Queries

Abbreviation	Term
SOC	System organ class
TART	Testicular adrenal rest tumor
TEAE	Treatment-emergent adverse event
TID	Three times per day
ULN	Upper limit of normal
ULQ	Upper limit of quantification
VAS	Visual analog scale
WHO	World Health Organization

## **1. INTRODUCTION**

The purpose of this statistical analysis plan (SAP) is to describe the planned analyses and data displays that will be prepared to summarize the data from the double-blind, placebo-controlled treatment period (Day 1 to Week 28; "DB period") and open-label treatment period (Week 28 to Week 52; "OL period") of the Phase 3 Study NBI-74788-CAH2006. Summaries of data from the open-label extension (OLE) for continued access to crinecerfont (starting after Week 52) will be described in a separate SAP.

This SAP was developed in accordance with International Council for Harmonization (ICH) E9 guidance. Data analyses described in this SAP will occur at 2 milestones in the study: after all subjects have had the opportunity to complete Week 28 and after all subjects have had the opportunity to complete Week 28 and after all subjects have had the opportunity to complete Week 52. The first analysis will include the final analysis of data through Week 28 and an analysis of all available safety and efficacy data up to Week 52. The second analysis will be the final analysis of data through Week 52. Decisions regarding each set of analyses will be made prior to the corresponding database lock and treatment unblinding and will be documented. Changes to the planned analyses described in this SAP will be statistically justified and described in the clinical study report (CSR). Further information related to study design and methodology can be found in the study protocol.

### 2. STUDY OBJECTIVES

The objectives of this study are:

#### **Primary:**

• To evaluate the efficacy of crinecerfont, compared with placebo, in reducing adrenal steroid levels during a glucocorticoid-stable period.

#### Secondary:

- To evaluate the efficacy of crinecerfont, compared with placebo, in reducing daily glucocorticoid dosage while maintaining adrenal androgen control.
- To evaluate the effect of crinecerfont, compared with placebo, on clinical endpoints associated with supraphysiologic glucocorticoid dosing and androgen excess.
- To evaluate plasma concentrations of crinecerfont and metabolites.
- To assess the safety and tolerability of crinecerfont.

## **3. STUDY DESIGN**

This is a Phase 3, randomized, double-blind, placebo-controlled study to evaluate the efficacy, safety, and tolerability of crinecerfont versus placebo administered bid with breakfast and evening meals for 28 weeks in approximately 81 pediatric subjects with classic CAH due to 21-hydroxylase deficiency. Eligible subjects will be randomly assigned in a 2:1 ratio (active:placebo) to either crinecerfont (25 mg bid via oral solution for subjects 10 to <20 kg, 50 mg bid via oral solution for subjects 20 to <55 kg, or 100 mg bid via oral capsules for subjects  $\geq$ 55 kg) or matching placebo (oral solution placebo for subjects <55 kg and oral capsule placebo for subjects  $\geq$ 55 kg). Dose assignment from Day 1 to Week 28 will be based on the subject's weight at Day 1. After the 28-week placebo-controlled treatment period, there will be a 24-week, open-label treatment period, during which all subjects will receive crinecerfont at doses based on their Week 28 body weight.

At Month 12 (Week 52), subjects will have the option to participate in an OLE. During the OLE, subjects will continue to receive crinecerfont at their weight-based dose, unless the subject has inadequate efficacy (in the opinion of the investigator), in which case their crinecerfont dose can be increased by doubling the evening dose. At Month 12, subjects can also elect to switch the crinecerfont formulation (oral solution or capsule) based on preference. Subjects have the option to remain in the OLE until crinecerfont becomes commercially available, the Sponsor elects to discontinue development of crinecerfont for CAH, or the Sponsor elects to discontinue the study.

## 3.1. Randomization

Eligible subjects will be randomized 2:1 to either crinecerfont or placebo on Day 1 using an interactive response technology (IRT). Randomization will be stratified by pubertal stage (Tanner breast or genital stage 1 or 2 versus 3, 4 or 5) and sex.

## 3.2. Blinding

Blinding will be maintained unless unblinding is necessary for subject safety. All subjects will be encouraged to complete follow-up even if an unblinding event has occurred. The subject, investigator, and all study center personnel will remain blinded to the subject's randomized treatment assignment(s) through database lock and unblinding of the Week 52 data. The Sponsor will remain blinded until all subjects complete the Week 28 visit and the database has been locked, at which time a limited number of Sponsor personnel will be unblinded to individual treatment assignments. Following this analysis, the subject, investigator, all study center personnel, and Sponsor personnel with direct contact with the site will continue to be blinded to the subject's blinded treatment assignment through database lock and unblinding of the Week 52 data.

An independent DMC will periodically review ongoing unblinded clinical and safety data to ensure the safety and well-being of the study subjects.

## **3.3.** Sample Size Considerations

The sample size of 81 subjects (54 in the crinecerfont treatment group and 27 in the placebo group) is based on a power calculation for the primary endpoint (change from baseline in serum androstenedione at Week 4). In the Phase 2 Study NBI-74788-CAH2001, the mean change from

Neurocrine Biosciences, Inc. Statistical Analysis Plan

baseline to Day 14 in androstenedione was -286.2 ng/dL with a standard deviation of 345.02 (pooled across dosing cohorts). Based on a 2-sample t-test with an effect size of 0.83, a sample size of 81 subjects will have greater than 90% power to detect a treatment difference at a 0.05 level of significance. With an effect size as small as 0.70, a sample size of 81 subjects will have greater than 80% power to detect a treatment difference at the same level of significance.

## 4. ENDPOINTS

The efficacy, safety, pharmacokinetic, patient and caregiver reported outcome, and other endpoints are listed below.

## 4.1. Primary Efficacy – DB Period

The primary efficacy endpoint in the DB period is the change from baseline in serum androstenedione at Week 4.

## 4.2. Key Secondary Efficacy – DB Period

Key secondary efficacy endpoints in the DB period are:

- Change from baseline in serum 17-hydroxyprogesterone (17-OHP) at Week 4
- Percent change from baseline in glucocorticoid daily dose (in hydrocortisone equivalents adjusted for BSA [mg/m^2/day]) at Week 28, while Week 28 serum androstenedione is ≤120% of the baseline value or ≤ ULN, according to sex and either age (for Tanner stage 1) or pubertal stage (for Tanner stages 2 to 5)

## 4.3. Secondary Efficacy – DB Period

Secondary efficacy endpoints in the DB period are:

- The achievement of a reduction in glucocorticoid daily dose to physiologic levels (≤11 mg/m²/day in hydrocortisone dose equivalents adjusted for BSA) at Week 28 while serum androstenedione is ≤120% of the baseline value or ≤ULN for sex and either age (for Tanner stage 1) or pubertal stage (for Tanner stages 2 to 5)
- Change from baseline in body mass index SDS (standard deviation score) at Week 28
- Change from baseline in mean 24-hour salivary 17-OHP at Week 28

In the subgroup of subjects not at adult height:

• Change from baseline in the ratio of bone age to chronological age (BA:CA) at Week 28

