#### **Prohibited and Restricted Medications**

The following medications are prohibited from 30 days before screening until the final study visit (or early termination):

- Orally administered glucocorticoids for indications other than CAH.
- Strong inducers of CYP3A4 or CYP2B6 except topically administered medications.
- Medications that affect cortisol or glucocorticoid metabolism (eg, phenytoin, mitotane, phenobarbital, strong CYP3A4 inhibitors such as ketoconazole, clarithromycin, cholestyramine, certain antivirals) except topically administered medications.

• Exogenous testosterone treatment (eg, patients with XX chromosomes and male gender identity).

The following medications have restrictions or requirements regarding use prior to and/or during the study:

- Gonadotropin-releasing hormone agonist therapy for treatment of precocious puberty is allowed if the dose is stable for at least 3 months prior to screening OR if there is evidence of adequate pubertal suppression according to the investigator's judgment.
  - Therapy should not be commenced or discontinued during the randomized phase of the study.
  - Discontinuation or start of therapy is allowed based on the investigator's judgment during the open-label phase of the study.
  - Subjects who were previously treated with these medications should have discontinued at least 3 months prior to screening.
- Growth hormone therapy and aromatase inhibitors (eg, anastrozole, letrozole, testolactone) are allowed if the dose is stable for at least 1 month prior to screening.
  - Therapy should not be commenced or discontinued during the randomized phase of the study.
  - Discontinuation or start of therapy is allowed based on the investigator's judgment during the open-label phase of the trial.
  - Subjects who were previously treated with these medications should have discontinued at least 1 month prior to screening.
- Anti-androgens (eg, spironolactone, flutamide) are excluded but oral contraceptives with anti-androgenic progestins (eg, drospirenone, cyproterone acetate) are allowed if the subject has been on stable therapy for at least 3 months prior to screening.
  - Subjects who were previously treated with oral contraceptives should have discontinued at least 3 months prior to screening.

If any of the above medications have been administered during the year preceding screening or during the study, their use should be captured on the Prior and Concomitant Medications eCRF.

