#### 13.6.1.4. Secondary Endpoints

Secondary endpoints will be compared by treatment group and will not be adjusted for multiplicity. Analysis methods for these endpoints will be described in the SAP. These analyses will be performed using observed data in the FAS.

The secondary endpoints include:

- The achievement of a reduction in glucocorticoid daily dose to physiologic levels (≤11 mg/m²/day in hydrocortisone dose equivalent adjusted for BSA) at Week 28 while serum A4 is ≤120% of the baseline value or ≤ULN for sex and either age (for Tanner stage 1) or pubertal stage (for Tanner stages 2 to 5)
- Change from baseline in body mass index SDS at Week 28
- Change from baseline in mean 24-hour salivary 17-OHP at Week 28
- Acceptability and palatability of the study drug at Week 4

In the subgroup of subjects not at adult height, secondary endpoints will also include:

- Ratio of the change in bone age from baseline to Week 28 to the change in chronologic age from baseline to Week 28
- Change from baseline in Bayley-Pinneau predicted adult height SDS at Week 52

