#### 9.5.4. Bone Age

The change from baseline to Week 28 in the ratio of bone age to chronological age (BA:CA) is a secondary endpoint in the subgroup of subjects not at adult height (female subjects with the most recent prior bone age <14 years and males with the most recent prior bone age <16 years at study entry) and not on gonadotropin-releasing hormone agonist therapy, growth hormone therapy, or aromatase inhibitors at study entry. BA:CA will be calculated at baseline and Week 28 by taking the bone age of the subject and dividing it by the chronological age of the subject at each respective visit. The change from baseline to Week 28 in BA:CA will be analyzed using an ANCOVA model, as described in Section 9.2.1. Descriptive statistics and LS means for change

from baseline to Week 28 in BA:CA will be presented by treatment group along with the LS-mean treatment difference, 95% confidence intervals, and p-value.

The change from baseline to Week 28 in the difference in bone age and chronological age (BA-CA) will also be analyzed using an ANCOVA model, as described in Section 9.2.1. Descriptive statistics and LS means for change from baseline to Week 28 in BA-CA will be presented by treatment group along with the LS-mean treatment difference, 95% confidence intervals, and p-value.

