### 14. DEVIATIONS FROM PROTOCOL PLANNED ANALYSIS

This section will document any deviations from the protocol planned analysis along with any assessments that were performed on study (and reviewed by the study site) but will not be summarized.

The following assessments were performed on study but will not be summarized:

- Physical examination results (excluding height, weight, and Tanner staging)
- CYP21A2 genotyping
- Pregnancy test
- Urine drug screen
- Urinalysis
- Glucocorticoid daily dose from eDiary

The following list includes all deviations from the protocol planned analysis:

- The Safety Analysis Set definition in the protocol specified that the subject must have postbaseline safety data during the double-blind placebo-controlled period. This part of the definition was removed from the SAP due to the potential issue of having a subject dosed with study drug and then becoming lost to follow-up.
- The Safety Analysis Set was split up into the DB Period Safety Analysis Set and the OL Period Safety Analysis Set.

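### The SAP replaces the protocol's bone-age secondary endpoint and narrows its population without declaring either change; the new measure can fall within an arm while bone age is still accelerating

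*SAP*

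**What the plan says.** Protocol 13.6.1.4, in agreement with the Synopsis, defines the endpoint as "Ratio of the change in bone age from baseline to Week 28 to the change in chronologic age from baseline to Week 28". The population is set by the lead-in "In the subgroup of subjects not at adult height, secondary endpoints will also include", with observed data in the full analysis set. Co-medication is not a restriction there. That section leaves analysis methods to the SAP.

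SAP 4.3 lists a different quantity: "Change from baseline in the ratio of bone age to chronological age (BA:CA) at Week 28". It places this in subjects not at adult height and mentions no co-medication.

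SAP 9.5.4 derives BA:CA "by taking the bone age of the subject and dividing it by the chronological age of the subject at each respective visit" and analyses the change by the ANCOVA of SAP 9.2.1. It limits the analysis to subjects who are also "not on gonadotropin-releasing hormone agonist therapy, growth hormone therapy, or aromatase inhibitors at study entry". The same section plans an ANCOVA of the change in BA−CA, the difference between bone age and chronological age.

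Protocol 9.10.1 permits these therapies at entry. Growth hormone and aromatase inhibitors "are allowed if the dose is stable for at least 1 month prior to screening"; GnRH agonists have a condition of their own.

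SAP 14 states: "The following list includes all deviations from the protocol planned analysis". Its two items both concern the safety analysis set.

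**The concern.** The protocol's ratio measures the tempo of skeletal maturation over the treatment period, and a value of 1 is one bone-year per calendar year. Change in BA:CA measures how the accumulated ratio moves, which depends on where the child started. Protocol 5.1 describes advanced skeletal maturation as a consequence of androgen excess, so baseline BA:CA above 1 is to be expected in many subjects. For them the two measures can point in opposite directions.

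The endpoint serves the objective on clinical consequences of androgen excess and supraphysiologic glucocorticoid dosing. A reader who takes a fall in BA:CA within an arm as slowed maturation could be wrong. A reader comparing the report with the protocol would find a different endpoint in a different population and no explanation in the section meant to provide one. SAP 4.3 and 9.5.4 also disagree with each other on who is analysed.

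**Working it through.** The plan gives no power or effect size for bone age, so there is no stated figure to reproduce.

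**Texts compared**

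| | Protocol 13.6.1.4 | SAP 4.3 | SAP 9.5.4 |
|---|---|---|---|
| Quantity | ΔBA/ΔCA | Δ(BA:CA) | Δ(BA:CA), plus Δ(BA−CA) |
| Not at adult height | yes | yes | yes |
| Users of the three therapies excluded | no | no | yes |
| Listed in SAP 14 | – | no | no |

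**Algebra.** Let B and C be baseline bone age and chronologic age, dB and dC their changes, and R = dB/dC the protocol endpoint. Then:

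- Δ(BA:CA) = (B + dB)/(C + dC) − B/C = dC × (R − B/C)/(C + dC)
- Δ(BA−CA) = dB − dC = dC × (R − 1)

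So BA:CA falls exactly when R is below B/C, whereas BA−CA falls exactly when R is below 1. The two signs disagree for every R between 1 and a baseline BA:CA above 1.

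**Numbers.** Week 28 is target day 196 (SAP 6.7), so dC = 196/365.25 = 0.537 years. The ages and tempos below are assumed, because the documents give none.

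| CA | BA | R | Δ(BA:CA) | Δ(BA−CA), years |
|---|---|---|---|---|
| 8 | 11 | 1.3 | −0.005 | +0.16 |
| 8 | 12 | 1.3 | −0.013 | +0.16 |
| 6 | 9 | 1.4 | −0.008 | +0.21 |
| 4 | 6 | 1.2 | −0.035 | +0.11 |
| 8 | 10 | 1.2 | −0.003 | +0.11 |
| 8 | 8 | 1.1 | +0.006 | +0.05 |

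First row in full: (11 + 1.3 × 0.537)/(8 + 0.537) = 11.698/8.537 = 1.370, against 11/8 = 1.375. BA−CA goes from 3.00 to 3.16. In the last row baseline BA:CA is 1 and the disagreement is gone.

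**Weighting by age.** A tempo difference of 0.1 contributes 0.1 × 0.537/(C + 0.537) to BA:CA: 0.0118 at age 4, 0.0063 at age 8 and 0.0043 at age 12. The ratio of ages 4 to 12 is 12.537/4.537 = 2.8. On the protocol scale the contribution is 0.1 at every age.

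**Randomised contrast.** The check was 4,000 simulated trials per scenario, with ANCOVA on treatment and baseline BA:CA. Assumptions: 40 and 20 subjects, ages 4 to 13, baseline BA:CA mean 1.35 (SD 0.2), tempo SD 0.6.

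- No effect, tempo 1.2 in both arms: rejection 5.5% for BA:CA and 5.4% for the protocol ratio. Mean Δ(BA:CA) on active was −0.010, despite a tempo above 1.
- Active 1.3 against placebo 0.9: mean Δ(BA:CA) on active was still −0.003.
- Across scenarios with a tempo difference of 0.4: power about 60–61% for BA:CA and 65–66% for the protocol ratio.

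**The case against.** The SAP's main comparison is a randomised difference in LS means. At a given baseline bone age and chronologic age, Δ(BA:CA) rises strictly with the bone-age gain, so a faster-maturing arm does not look slower than its comparator. The simulation shows no inflation of type I error. This stands. A reader might infer that the substitution could make crinecerfont appear to slow bone age relative to placebo when it does not. The documents do not support that, nor do they suggest the measure was chosen for its result: SAP 6.1 says the analyses were defined before database lock.

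The BA−CA analysis in SAP 9.5.4 is also a real safeguard. Since R − 1 = Δ(BA−CA)/dC, over a common interval it is close to a linear rescaling of the protocol endpoint, and it would expose the acceleration in every row above where BA:CA falls. It is not, however, the named secondary endpoint.

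Excluding subjects by therapy at entry does not break randomisation, and Protocol 9.10.1 says these therapies should not be started or stopped during the randomised phase. It is a question of population and documentation, separate from the sign problem. The SAP model also carries sex, pubertal stage and baseline BA:CA, which partly stand in for age.

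Finally, the endpoint lies outside the fixed testing sequence and its p-value is nominal (SAP 9.5).

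None of this accounts for the silence of SAP 14. The protocol left the methods to the SAP, not the definition of the endpoint.

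**Conclusion.** The SAP changes both the quantity and the population of a protocol-named secondary endpoint, never analyses the protocol's version, and lists neither change. This follows from the texts alone.

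The consequence for interpretation is narrower. Within-arm values of BA:CA can fall while bone age advances faster than one year per year, for any child whose tempo lies between 1 and a baseline BA:CA above 1. This matters for the LS means shown by arm at Week 28. It matters more for the descriptive Week 52 summaries in SAP 10.5, which have no concurrent placebo group, although BA−CA is summarised there too. The randomised estimate keeps its direction at given baseline ages but gives more weight to younger children, about 2.8-fold between ages 4 and 12.

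The numerical illustrations rest on assumed ages and tempos. The documents give neither a baseline BA:CA distribution nor a count of co-treated subjects, so the size in this trial cannot be stated. Control of type I error for the primary and key secondary endpoints is unaffected. The point should be corrected, but it does not threaten the trial's main conclusions.

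**What to change.** Analyse ΔBA/ΔCA at Week 28 as the named secondary endpoint, using observed data from all full-analysis-set subjects not at adult height. The model in SAP 9.2.1 cannot be applied unchanged, because this ratio has no baseline value to serve as covariate. Specify an ANCOVA with treatment, the two stratification factors and a stated covariate, such as baseline BA:CA, or baseline bone age and chronologic age together.

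Keep change in BA:CA, change in BA−CA and the subgroup not on the three therapies as supplementary analyses. Make SAP 4.3 and 9.5.4 agree on the population. List and justify in SAP 14 any difference from the protocol that remains.

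The cost is SAP wording and one derivation from bone ages and dates already collected. A loss of precision should not be assumed: under the simulation's assumptions the protocol ratio had slightly more power than BA:CA.
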